Primary Hypothesis (H₁): Among patients with >5% 10-year risk for a cardiovascular event, there will be at least a 2.0% difference between GPC and usual care in reduction of predicted rate of fatal or non-fatal MI, as estimated by the Framingham Risk Score (FRS).

Aim 2: To determine the effectiveness of GPC (compared to VA usual care) in: (a) increasing physical activity, and (b) making dietary improvements.

H_{2A}: Compared to usual care, GPC will lead to an increase in physical activity as measured by International Physical Activity Questionnaire.

 H_{2B} : Compared to usual care, GPC will lead to a decrease in saturated fat intake, as measured by Food Frequency Questionnaire.

Aim 3: Among intervention patients, to determine the role of group cohesion in predicting the success (or lack thereof) of GPC.

H_{3A}: Strong group cohesion, as measured by the Group Cohesion Scale, will predict improvement in FRS among patients receiving the GPC intervention.

Aim 4 (exploratory): To measure the cost of the GPC intervention.

B. BACKGROUND AND RATIONALE.

B.1. Cardiovascular (CV) event prevention. Cardiovascular disease (e.g., myocardial infarction, cerebrovascular accident) remains the single most important public health problem in the United States (15), and cardiovascular disease is a leading cause of death among VA users (16). CV events are mostly considered preventable by more appropriate treatment of CV risk diseases (eg, hypertension (HTN) and hyperlipidemia (HL)). Modification of behavioral risk factors (eg, smoking cessation, increased physical activity, stress reduction) is also key to CV event prevention, both by direct effect on health as well as by improving the risk diseases above. Improving the provision of prevention services is a primary focus of the Secretary's New Models of Care Transformational Initiative (17). However, prevention of CV disease has been challenging to achieve, as can be seen by continued inadequate risk factor management; a fifth of Americans (a greater proportion of VA users) continue to smoke, only half of people achieve physical activity goals, and more than a third of VA users do not achieve treatment targets for blood pressure and/or cholesterol (18-21). The evaluation of alternative strategies to improve CV disease prevention is the focus of our CREATE.

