B.6.b. Multifactorial behavioral interventions can improve CV risk behaviors among Veterans. [name] led CouPLES, a spousal support intervention to improve cholesterol (56). The intervention had some similarities to our proposed approach in that patients were allowed to choose from a menu of behaviors to potentially lower their cholesterol, and a phone interventionist trained in motivational interviewing helped patients set goals regarding CV risk behaviors (diet, activity, med adherence). CouPLES was a null study on its primary outcome, LDL-cholesterol. However, there was a moderate, near-significant increase in number of patients reaching physical activity goals compared to usual care (20% greater increase, p=0.06) and a modest, statistically significant decrease in total (12g/d larger decrease compared to control, p= 0.02) and saturated (3g/d, p=0.02) fat intake. These results show our ability to improve CV risk behaviors among Veterans using complex interventions, and highlight the importance of using composite outcomes more sensitive to subtle multi-behavioral changes than individual clinical outcomes (eg LDL-C, BP)

B.6.c. Group interventions can improve Veterans' Health, and potentially be cost effective. Drs. [name] and [name] led a randomized controlled trial at two VAMCs of Shared Medical Appointments for Diabetes and the economic analysis of that trial, respectively (11). The results showed that Shared Medical

Appointments improved systolic blood pressure 7 mmHg compared to usual care, and LDL-cholesterol by 9 mg/dl; there was a modest, not statistically significant improvement in hemoglobin A1c (0.3 percentage points; p=0.16). The economic analysis showed statistically significant improvement in per patient cost and in hospitalizations in the second year after the end of the intervention when compared to usual care. Similarly, [name] co-led a family caregiver intervention using PST, among other components, and found that the cost of care for Veteran care-recipients was on average approximately \$2700 less than Veterans receiving usual care (57). These results show that (1) group strategies have the potential to save money, and (2) we can deliver a multi-site group intervention randomized trial in the VA. Note that the group visit strategies here are totally different from the one we propose; see section D.5.

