D.4.a. Randomization. The project's masters-level statistician will maintain a computer generated, patient randomization sequence separate from the site of patient enrollment. The group assignment will be communicated to the opposite site RA (ie, Durham patients will receive a randomization call from the Upstate NY RA, and vice-versa). That RA will make the phone call at the appointed time, and explain the implications of the arm assignment to the subject. This will allow the local RA to remain blinded to arm assignment for follow-up evaluation. Randomization will be stratified by site and gender. Patients randomized to the GPC arm will be offered a choice of one of a few possible half-days for their group session to meet, and that choice will lead to the patient's assignment to a particular GPC group.

D.5. Intervention. The GPC intervention will be delivered to patients in the active arm. The basic structure is that of a group problem-solving intervention, with interval phone calls delivered to check in on goal progress and reinforce group learning. Groups will meet monthly for 6 months, and each patient will be called once between each group session. Based on our experience with delivering problem solving groups (JN), each group will consist of 10 patients. In general, problem-solving principles will represent the content of the group sessions. Problem solving theory is described in greater detail above (B.4). Again, problem solving intends to teach patients to overcome internal barriers to healthful behaviors. We will directly assess the effects of problem solving in our intervention by use of the CD-RISC (D.8.b.iii.b).

The problem solving orientation will be combined, at all group sessions, with the typical self-efficacy training used in SMGs, so that patients will be taught simultaneously to overcome both internal and external barriers. Similar to our prior studies (eg, CouPLES (56)), participants will be asked to develop personal goals related to CVD-related behaviors (e.g., smoking and weight reduction). We will directly assess the coaching effects by measuring self-efficacy across chosen behaviors using the Patient Activation Measure (PAM, D.8.b.ii.a below)

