about the time and place. Our experience is that the half-day will be set and the first visit will occur within 2-4 weeks of the enrollment visit for each patient. Groups will meet every month for 6 months. The same 10 patients will meet each time with the same group facilitators, on the half-day of the week chosen as described above. Group sessions will last 90 minutes; the first 20 minutes are set aside for social interaction as a means to engage the patients (11), and the remaining 70 minutes are for content delivery (see D.5.d). Phone calls will be made once to each patient in the interval between group sessions.

D.5.d. Attendance Enhancement Strategies. Above and beyond the usual encouragement to attend group sessions, we will attempt to increase attendance by having patients sign attendance contracts. Behavioral contracts have been shown in randomized, controlled trials to improve attendance to group sessions (66, 67). Patients will sign the attendance contract immediately upon arriving to the first group session. In addition to contracts, we will offer a cash reimbursement of \$25, similar to the expected travel pay for a clinic visit for a patient living 20 miles away, for patients attending group sessions. In our hands, session attendance has been approximately 80% using this combined approach (11).

D.5.e. Group Session Content. The group session content is taken from pre-existing group problemsolving session content, and modified to reflect both the focus on cardiovascular prevention rather than on mental health concerns as well as the self-efficacy training orientation.

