D.8.b.ii. Cost. The intervention, while not enormously expensive because of its use of relatively affordable personnel, will not be trivially inexpensive. In considering the implementation of GPC, stakeholders will want to know whether they are getting appropriate "bang for their buck." While full cost-effectiveness analysis is beyond the scope of this proposal, we will perform simple direct cost analysis of the intervention so that appropriate cost-benefit analyses can be undertaken under separate funding should the intervention be effective. Effects on utilization will not be considered as part of this proposal. We will measure only intervention-related labor for this study; our prior works shows that intervention-related capital costs are trivial in similar interventions (11). To measure hours required for the intervention, 4 people will carefully log their hours in delivering the intervention (including development) in a spreadsheet. The group interventionist will log time associated with performing and preparing for group sessions; the LPN will log phone call time and any time associated with documentation for the phone call; the RA will log only that time spent scheduling group sessions; and [name] will log supervisory time. Costs will be determined by multiplying these hours by the hourly grade/scale rate for the relevant person (using the appropriate fringe benefits multiplier). Time spent on research activities (ie, data collection and management) will not be logged.

D.8.b.iii. Process variables. We are interested in the contribution to GPC's efficacy, if any, of three process variables; group dynamics, and individual patient resilience.

D.8.b.i.a Self-efficacy. Self-efficacy involves a "judgment of one's abilities to produce given attainments." Individuals who believe they possess the skills necessary to achieve goals are more likely to adopt healthy behaviors (40, 41). Measures that measure self-efficacy across a range of behaviors are hard to find; our choice is the Patient Activation Measure (PAM), a 13-item measure that assesses patients' knowledge, skills, beliefs and confidence for managing their health (74). As a primary outcome measure in clinical trials, improvement in PAM scores has led to improvement in various self-management behaviors; a 4-6 point difference is felt to be clinically meaningful (75-78).

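### The labor-only cost rule for exploratory Aim 4 leaves out the 25-dollar cash for attending group sessions, and the reason given for the rule does not cover that payment

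*Combined protocol and SAP*

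**What the plan says.** The Specific Aims list "Aim 4 (exploratory): To measure the cost of the GPC intervention". D.8.b.ii then describes a limited direct cost analysis and puts full cost-effectiveness analysis and effects on utilization out of scope. It gives the scope rule and its reason in one sentence: "We will measure only intervention-related labor for this study; our prior works shows that intervention-related capital costs are trivial in similar interventions". Four people log hours, and cost is logged hours times the pay rate times a fringe multiplier. Development hours are included and only research time is excluded. The result is meant to support later cost-benefit work if GPC proves effective.

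D.5.d (Attendance Enhancement Strategies) belongs to section D.5 on the intervention. After describing attendance contracts it says "In addition to contracts, we will offer a cash reimbursement of" 25 dollars, "similar to the expected travel pay for a clinic visit for a patient living 20 miles away, for patients attending group sessions". It then reports about 80% session attendance in the team's earlier work with contracts and cash combined.

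**The concern.** The aim names the cost of the intervention, and the session cash is one of the intervention's listed components. A cost built only from hours and pay rates has no place for it. The single reason given for the narrow scope concerns capital items, and cash handed to patients is not a capital item. The omission is therefore open in its effect but not argued for.

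What is at stake is how the cost figure can be used. Any GPC effect will have been obtained with the cash on offer. If a later cost-benefit analysis pairs that effect with a cost that leaves the cash out, its two sides describe different packages. A smaller question is whether one-off development hours, which the rule counts, will be visible apart from the labor that recurs each time a group is run.

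**Working it through.** The plan states no GPC cost per patient, so there is no cost figure to reproduce. The check is of what the rule includes, and then of the size of the omitted item.

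**Does the rule cover the cash?**
- D.8.b.ii counts group preparation and delivery, calls and their documentation, scheduling, supervision, and (in a general clause) development. All of these are hours.
- D.5.d is a payment to patients. It enters neither the hours nor the pay rates.
- It is also distinct from the research payment in D.4, which is 50 dollars at each of three measurement visits in both arms (3 × 50 = 150 dollars, the maximum stated there). The session cash goes only to patients attending groups, so only to the GPC arm.

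**Inputs**
- Payment: 25 dollars (D.5.d). Unlike D.4, D.5.d does not say whether it is paid each time or once. The comparison with travel pay for a clinic visit suggests each time.
- Sessions: six. D.5 says "Groups will meet monthly for 6 months, and each patient will be called once between each group session", and D.5.e describes sessions 1 to 6.
- Attendance: about 80% (D.5.d), from earlier work. That it carries over to GPC is an assumption.

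**Omitted cash per GPC patient** = 25 × number of payments

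| Case | Calculation | Dollars |
|---|---|---|
| Attends no session | 25 × 0 | 0 |
| Attender, paid once | 25 × 1 | 25 |
| Paid per session, 80% attendance on average | 25 × 6 × 0.80 | 120 |
| Paid per session, all six attended | 25 × 6 | 150 |

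With about 200 patients in the GPC arm (400 planned, equal arms assumed), the last three rows give 25 × 200 = 5,000, 120 × 200 = 24,000 and 150 × 200 = 30,000 dollars. The 5,000 assumes that every patient attends at least once.

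**Share of total cost.** This would need hours for preparation, documentation, scheduling, supervision and development, together with pay rates. The documents give none of these, so the share cannot be computed.

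**Development hours.** D.8.b.ii includes development in the log, but the role-by-role list that follows does not mention it, and nothing says it will be reported separately. The number of hours is not given. H hours spread over about 200 patients add H/200 hours each; an assumed 100 to 500 hours would add 0.5 to 2.5 hours per patient.

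**The case against.** The strongest reply is that the scope is declared. The aim is exploratory, D.8.b.ii promises only a limited cost exercise, and it says plainly that labor alone will be measured. Other non-labor items, such as the mailed primer (D.4) and the purchased motivational interviewing training (D.7), fall outside the rule too. The cash is also likened to travel pay, so a facility adopting GPC might not bear it as a new cost. Because the amount is published, a later analyst could add it once the payment basis and attendance were known.

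Most of this stands. It limits the point to a reporting improvement and means that the cost with cash added would still not be a full intervention cost. It does not supply a reason for leaving out a payment that the protocol lists under the intervention and ties to its attendance figure. The payment basis that a later analyst would need is also not stated.

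A reader might infer more than the documents support:
- *That the cash rivals the labor cost.* Setting it against scheduled session and call time alone would exaggerate it, because D.8.b.ii also logs several other kinds of hours. D.5.c speaks of facilitators in the plural, so even the contact hours are uncertain.
- *That the protocol contradicts itself by relying on earlier group visits it elsewhere calls very different.* That remark in B.6.c concerns care strategies. It does not show that capital costs differ, and it bears on neither the cash nor the development hours.
- *That start-up and recurring costs will be impossible to tell apart.* The log is a spreadsheet describing activities by person. The plan is silent on separate reporting, which does not show that the hours will be merged beyond recovery.
- *That the Aim 4 figure will be too low overall.* Omitting the cash lowers it, while counting one-off development hours raises a per-patient figure. The net direction is unknown.

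**Conclusion.** The point holds as a cheap improvement to an exploratory aim. Followed as written, D.8.b.ii yields a GPC cost that omits an outlay the protocol itself places in the intervention, and the stated reason does not reach that outlay. The amount is 0 to 150 dollars per GPC patient: 25 dollars for an attender if paid once, and about 120 dollars on average if paid per session. The 120 rests on two assumptions: payment at every session, which is suggested but not stated, and 80% attendance carried over from earlier work. Whether routine VA delivery would carry the payment is left open by the documents, so neither the figure with it nor the figure without it is the single correct one. The development-hours matter is secondary, since the plan counts those hours and merely does not say how they will be shown. The primary and secondary analyses, the sample size and the safety conclusions are unaffected.

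**What to change.** In D.8.b.ii:
1. State whether the 25 dollars is paid per session or once.
2. Tabulate the session payments actually made as a separate line, and report cost per GPC patient with and without that line.
3. As a minor addition, tag development hours in the existing spreadsheet and report them as a one-off line, apart from recurring delivery, scheduling and supervision labor.

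The cost is slight: a little more tabulation, one more column in the hours log, and a record of session payments, which the documents do not describe. Tagging is best done when the hours are logged. The figure with the cash included will look less favorable, and the scope should still be described as partial.

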fostering "resilience." A recent article employing systematic review principles, concept analysis, and stakeholder consultation broadly defined resilience as the "process of effectively negotiating, adapting to, or managing significant sources of stress or trauma" (Windle, 2011, p. 152). Resilience is also associated with better outcomes among patients with diabetes (55). By teaching patients to overcome internal barriers, to master better problem-solving techniques, and to be more resilient, we expect to prepare them to be better able to deal with the sociostructural (external) barriers that they will face and make better use of the strategies they use to achieve their stated personal goals. In essence, we will use problem-solving to "prime" patients for using traditional goal-setting approaches to change behavior, with the expectation that this will enhance the success of these approaches.

Our study measures were selected to reflect both the processes and outcomes of behavior change. Our primary outcome will be Framingham Risk Score (FRS), a well-validated predictor of cardiovascular events (D.8.a below), which should be lowered with any number of healthful behavior changes (eg healthier eating, increased physical activity, smoking cessation). We will also measure those behavior changes directly. Those changes, in turn, should be increased to the extent that patients are high in self-efficacy, have increased their resilience, and feel as though they have been supported by the peer group (self-efficacy, resilience, and group cohesion are our process outcomes).

B.6. Preliminary studies.

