D.8.b. Secondary measures. Several measurements will be made that are not inputs to the primary outcome (FRS). Some are behavior change outcomes of the study, some are designed to assess possible mechanisms of action of the intervention, and some are potential analytic covariates or population descriptors.

D.8.b.i Secondary Outcomes. All secondary outcomes will be ascertained at all time points. For each outcome, the listed reference(s) refer to studies validating the measures. We recognize that, given that different patients may choose different behaviors to change, that we will have diminishing power to see change in these behaviors; nonetheless, the demonstration of modest, potentially not quite significant change across a number of behaviors is important confirmation of how any change in FRS may have occurred.

D.8.b.i.a Exercise. One of the goals of the intervention will be to increase the amount of leisuretime exercise performed by those patients who are not exercising to appropriate standards. Leisure-time activity will be measured by the International Physical Activity Questionnaire (IPAQ), a well-validated physical activity inventory commonly used in studies with the goal of changing leisure-time activity (70). Results can be expressed as metabolic equivalents. We selected this measure because it has been validated against a more objective method (i.e., accelerometer), yet it has the advantage of being convenient and cost effective as a self-report method.

D.8.b.i.b. Caloric Intake. The sentinel impact of diet on cardiovascular risk is weight loss (71), which leads to significant improvement in blood pressure and lipids. Therefore, one measure of salutary diet

change in this study will be weight. We will measure height at baseline, allowing us to use body mass index as an estimate of appropriateness of weight for each individual. To capture salutary dietary changes not encompassed by weight loss (e.g., decreased fat intake), we will use the Block Brief 2000 Food Frequency Questionnaire (FFQ), which was developed from the National Health and Nutrition Examination Survey (NHANES) III food intake data (72, 73). The questionnaire is a reliable and valid self-report dietary intake instrument, and provides information on intake of macronutrients, which will be our dietary outcomes. We will measure saturated fat as our dietary change outcome.

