D.8.b.iii.a. Group Cohesion. We will measure patients' perception of their cohesion with the group in intervention patients only by using the Group Cohesion Scale. The GCS is a 6-item measure with good internal validity (53) and correlation to individual performance in workplace settings (35). We will evaluate whether GCS scores are related to improvements in FRS among intervention patients.

D.8.b.iii.b. Resilience. We will evaluate whether Connor-Davidson Resilience Scale (CD-RISC) scores are related to improvements in the primary and secondary outcomes (79). This 25-item scale is one of the most widely used scales to measure resilience in physical health settings. A methodological review of existing resilience measurement scales (15) indicated that the Connor-Davidson Resilience scale (full 25-item version) was one of three measures that received the best psychometric ratings

D.8.b.iii.c.. Med adherence. A 3-item validated questionnaire

D.8.b.iii.d. Social Problem-Solving inventory A 25-item questionnaire.

D.8.b.iv. Covariates. We will measure a number of demographic factors at baseline only that may affect response to the intervention, including race, age, marital status, education level, gender, adequacy of annual income, and number of people living in the household. All will be measured at baseline by self-report.

Body Mass Index (BMI): Patient is weighed using a digital scale that provides a print out. The patient's weight is entered from the printout (valid range is from 100-700 lbs). Height is measured twice and entered twice. If two heights are more than 0.5" different, then height is measured a 3rd time. Weight is then entered a 2nd time from the printout (i.e., a real-time double data entry). If the two weights are not exactly the same, the RA chooses the correct weight. The two closest heights & the correct weight are used to calculate BMI. BMI will be collected in person at the enrollment and 6 month visits with the research assistant.

D.8.b.v. Other Measures. Short Form Health Survey (SF-1)³⁶: question 1 on self-rated general healthPatient Heath Questionnaire (PHQ-8)³⁷ to measure current depression Tobacco Use/Smoking: Measure from the CDC Adult Tobacco Survey³⁸ asking if they have ever smoked (100 cigarettes in your entire lifetime) and a

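### The association stated for CD-RISC cannot show that resilience contributed to GPC's efficacy, and D.9 names no between-arm model for CD-RISC and none clearly for PAM

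*Combined protocol and SAP*

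**What the plan says.** **The question.** D.8.b says of the secondary measures that "some are designed to assess possible mechanisms of action of the intervention". D.8.b.iii then states: "We are interested in the contribution to GPC's efficacy, if any, of three process variables". It announces three variables and names two, group dynamics and resilience. B.5 supplies the third: "self-efficacy, resilience, and group cohesion are our process outcomes".

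**Resilience.** D.8.b.iii.b states: "We will evaluate whether Connor-Davidson Resilience Scale (CD-RISC) scores are related to improvements in the primary and secondary outcomes (79". It gives no arm term, analysis set or time point, and does not say whether the score or its change is meant. D.5 adds: "We will directly assess the effects of problem solving in our intervention by use of the CD-RISC (D.8.b.iii.b". That sentence points back to D.8.b.iii.b and gives no model.

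**Self-efficacy.** D.5 states: "We will directly assess the coaching effects by measuring self-efficacy across chosen behaviors using the Patient Activation Measure". D.5 cites the PAM section as D.8.b.ii.a. The section itself is numbered D.8.b.i.a, the number already used for exercise, and it sits under the process-variables heading D.8.b.iii. It states no analysis.

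**D.9.** D.9.a summarizes all study variables overall and by arm. D.9.d models FRS. D.9.e, headed as the Aim 2 analyses, applies the same approach to the secondary outcomes; Aim 2 covers physical activity and diet. D.9.f covers group cohesion, in intervention patients only, and is labeled exploratory. No indirect-effect analysis appears.

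**The concern.** A process variable contributes to GPC's efficacy only if two things hold: GPC changes the variable, and that change alters the outcome. Relating CD-RISC scores to improvement addresses neither link by randomization. It is a comparison between patients. If more resilient patients improve more in whichever arm they are in, the association is positive even when GPC did nothing to resilience.

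The first link can be tested with the trial's own randomization, because controls follow the same scientific protocol (D.6) and the battery is taken at baseline, 6 and 12 months (D.4). The plan does not name that test.

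What is at stake is the explanation of the result. Section C says that VA problem-solving leaders will be informed about the use of problem solving in prevention, and Section E plans rapid dissemination if GPC works. A statement that resilience contributed, resting on the association alone, could misinform both.

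**Working it through.** **1. Sample available (D.9, Sample Size Calculations).** Inputs: two-sided α = 0.05, power 80%, SD of FRS change 6.3, difference 2.0, group size m = 10, ICC ρ = 0.03, with the design effect in the GPC arm only.

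- n per arm = (1.960 + 0.842)² × {6.3² + 6.3² × [1 + 9 × 0.03]} / 2.0²
- = 7.849 × 39.69 × 2.27 / 4 = 176.8, so 177, against the stated 180 (within 2%).
- 360 / 0.90 = 400, as stated.

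The plan's figure is reproduced. It leaves 360 evaluable patients, 180 of them in GPC. The documents give no figure for the process-variable analysis itself.

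**2. How often the association is significant when the effect through resilience is zero.** Suppose GPC has no effect on CD-RISC, and CD-RISC correlates r with improvement within each arm for reasons unrelated to GPC. The values of r are assumptions. By Fisher's z, ignoring clustering, power ≈ Φ(λ − 1.96) + Φ(−λ − 1.96), with λ = atanh(r) × √(n − 3). Here √357 = 18.89 and √177 = 13.30.

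| Assumed r | atanh(r) | λ, n = 360 | Significant, n = 360 | λ, n = 180 (GPC only) | Significant, n = 180 |
|---|---|---|---|---|---|
| 0.05 | 0.0500 | 0.946 | 16% | 0.666 | 10% |
| 0.10 | 0.1003 | 1.896 | 47% | 1.335 | 27% |
| 0.15 | 0.1511 | 2.856 | 81% | 2.011 | 52% |
| 0.20 | 0.2027 | 3.831 | 97% | 2.697 | 77% |

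Both sample sizes are shown because D.8.b.iii.b does not fix the analysis set.

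**3. Check by simulation.** 4,000 trials per scenario, 180 per arm, ICC 0.03 in GPC groups of 10, no GPC effect on resilience, a common cause producing the correlation, and GPC improving FRS by 2.0 points through other routes.

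| Assumed r | Association significant | Arm difference in resilience significant | Both links significant |
|---|---|---|---|
| 0.1 | 47% | 4.5% | 1.8% |
| 0.2 | 96% | 5.1% | 5.0% |
| 0.3 | 100% | 4.5% | 4.5% |
| 0.5 | 100% | 4.9% | 4.9% |

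The mean estimated indirect effect was about 0.00 FRS points throughout. With no GPC effect on FRS either, the association was significant in 47%, 97%, 100% and 100%. The arm comparison stays near its nominal 5%; the association does not respond to whether GPC changed resilience.

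**4. Coverage of the two scales in D.9.**

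| | CD-RISC | PAM |
|---|---|---|
| Effect to be assessed (D.5) | yes | yes |
| Association with outcomes | D.8.b.iii.b | none stated |
| Summary by arm | D.9.a | D.9.a |
| Between-arm model | none named | unclear; depends on whether D.9.e is meant to include it |
| Indirect-effect model | none | none |

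**The case against.** **The plan does intend to look at effects.** D.5 says CD-RISC will be used to assess the effects of problem solving, and D.9.a will show both scales by arm. A reader might infer from D.8.b.iii.b that the association is all that is planned, or that a GPC effect on either scale would go unnoticed. The documents do not support that. What is missing is a named between-arm estimate with an interval.

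**PAM may be covered.** Its printed number would place it among the secondary outcomes to which D.9.e applies. Its position under process variables and the Aim 2 heading of D.9.e point the other way. That PAM has no planned analysis is therefore too firm; the coverage is unclear.

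**Timing.** One might argue that score and FRS come from the same visit, so that direction is open. D.8.b.iii.b does not say which score is used, and a baseline score would precede the change in FRS.

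**The percentages are power figures.** They assume a real correlation and give the chance of detecting it. If the result is reported as a relation, it is correct. It misleads only if reported as a contribution. A reader might take 97% as a false-positive rate of the plan; it is not, and at r = 0.05 the figure is 16%.

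**Standing in the trial.** Neither scale is in an aim or hypothesis, and D.8.b.iii speaks of a contribution only if there is one. This limits the weight of the point. It does not remove the mismatch between the question and the stated analysis.

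**Conclusion.** The point holds as a limited one. The CD-RISC association cannot answer the question posed in D.8.b.iii, and D.9 names no between-arm model for CD-RISC and none clearly for PAM. The logic needs no particular correlation. The size, about 16% to 97% significant with 360 patients and a zero effect through resilience, rests on assumed correlations of 0.05 to 0.20 and is an illustration only.

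The consequence is confined to statements about mechanism. The primary analysis and the sample size stand. A reader might extend the criticism to all the process variables, but group cohesion is measured only in GPC patients, so no arm comparison is possible, and its Aim 3 analysis is already labeled exploratory.

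**What to change.** 1. In D.9, apply the D.9.d constrained longitudinal model, with its group random effect, to CD-RISC and PAM. Report the GPC-versus-usual-care difference and its interval at month 6, with month 12 secondary. Write the time terms out in full: the D.9.d equation as it reads here shows no month-6 main effect, which may only be lost text.
2. Correct the PAM section number and its cross-reference, name the third process variable in D.8.b.iii, and say whether D.9.e includes PAM.
3. In D.8.b.iii.b, state which score, visit and patients are used, and call the association descriptive. Do not claim a contribution to efficacy unless GPC is shown to change the scale. That condition is necessary but not sufficient.
4. Describe an arm difference in either scale as an effect of the whole package. Groups, problem solving and calls are delivered together, so the trial cannot credit one of them.
5. Optionally, add an indirect-effect analysis labeled exploratory. It should address month-6 FRS, the primary endpoint, with month 12 as a supplement: the intervention ends at 6 months and D.4 leaves open whether effects last. It must state the assumption of no unmeasured confounding between scale and outcome.

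The cost is SAP wording and two more fits of a model already planned, with no new data if both scales are in the common battery, as D.4 and D.6 imply. Step 5 takes more work and rests on an assumption that the trial cannot check. Rewording D.8.b.iii as a question of association only would also remove the mismatch, but would leave the randomized comparison unused.
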